3.3.3 Exclusion criteria

- 1. Presence of active ocular conditions with or without visual impairment due to any causes (e.g. cataract, chorioretinal macular lesion, amblyopia, active diabetic retinopathy, uncontrolled glaucoma, active inflammation or infection, etc.) in one eye or both eyes at the screening phase that may interfere with the ocular assessments or analyses and interpretation of the results from this study, in the clinical judgment of the investigator.
- 2. Planned ocular treatment (e.g. intravitreal antivascular growth factor, corticosteroids) or surgery during the study period.
- 3. Current or planned use of ocular or systemic corticosteroids.
- 4. Current or planned use of medications known to be toxic to the retina, lens, optic nerve (e.g. choroquine/hydrochoroquine, chlorpromazine, tamoxifen, desferoximine, etc.).
- 5. Subjects treated with more than two antipsychotic medications (including more than two dosage forms).
- 6. Subjects needing to take long-acting hypnotics or anxiolytic (i.e. Diazapam).
- 7. Subjects taking medications that are known to be strong or moderate CYP1A2 inhibitors (For a list of strong and moderate CYP1A2 inhibitors please consult the ISF Section 11 "Safety Information").
- 8. Dementia in AD patients, secondary to other disorders (based on clinical data and/or current laboratory findings and/or on a pre-existing cranial MRI or CCT which is not older than 12 months prior to screening visit)*, for example: small vessel disease, neurosyphilis, craniocerebral trauma.
 - *If it is not already available then a CCT scan must be performed at screening.
- 9. Neurological disease (other than Dementia of Alzheimer Type such as: Lewy body dementia primary diagnosis, Huntington's disease, Parkinson's Disease encephalitis, epilepsy, vascular or multi-infarct dementia, stroke, congenital mental deficiency, or multiple sclerosis), or mental retardation.

- 10. For AD patients, the following drugs are prohibited for 3 months prior to randomization and for the duration of the trial:
 - a. tricyclic antidepressants,
 - b. antidepressants that are monoamine oxidase inhibitors,
 - c. neuroleptics with moderate or greater anticholinergic potency (e.g., chlorpromazine, fluphenazine, loxapine, perphenazine, thioridazine),
 - d. anticholinergic medications.
 - e. Intake of St. Johns wort, Carbamazepine and extracts from Ginko as they are relevant CYP2C19 inducers.

The following drugs may be given as needed if the total daily dose was stable 8 weeks prior to randomization and is expected to be stable for the duration of the trial:

- a. neuroleptics listed in Section 4.2.2,
- b. benzodiazepines and sedatives listed Section 4.2.2.
- 11. Substantial concomitant cerebrovascular disease (defined by a history of a stroke/intracranial haemorrhagia temporally related to the onset of worsening of cognitive impairment), per investigator judgment.
- 12. Any suicidal ideation of type 4 or 5 in the Columbia Suicidal Severity Rating Scale (C-SSRS) in the past 3 months (i.e. active suicidal thought(s) with intent but without specific plan, or active suicidal thought(s) with plan and intent).
- 13. Any suicidal behavior in the past 2 years (i.e. actual attempt, interrupted attempt, aborted attempt, or preparatory acts or behavior).
- 14. History or diagnosis of symptomatic and unstable/uncontrolled gastrointestinal, hepatic, renal, respiratory, cardiovascular, metabolic, immunological, haematological or hormonal disorders.

15. For female subjects:

Pre-menopausal women (last menstruation ≤1 year prior to informed consent) who:

- are nursing or pregnant or
- are of child-bearing potential and are not practicing an acceptable method of birth control, or do not plan to continue using this method throughout the trial until 28 days after the last treatment administration, and do not agree to submit to periodic pregnancy testing during participation in the trial. Acceptable methods of birth control include tubal ligation, vasectomized partner, transdermal patch, intra uterine devices/systems (IUDs/IUSs), combined estrogen-progestin oral contraceptives as well as implantable or injectable hormonal contraceptives unless they are a moderate to strong CYP1A2 inhibitor see Section 4.2.2.1. Complete sexual abstinence (if acceptable by local health authorities) is allowed when this is in line with the preferred and usual lifestyle of the subject. Periodic abstinence (e.g., calendar, ovulation, symptom-thermal, post-ovulation methods) and withdrawal are not acceptable methods of contraception. Double barrier methods are permissible (if acceptable by local health authorities).

Doc. No.: c02218444-07 Trial Protocol Revision 3 Page 31 of 101

For male subjects:

Men who are able to father a child, unwilling to be abstinent or use adequate contraception for the duration of study participation and for at least 28 days after treatment has ended.

- 16. Known history, or new diagnosis per screening labs, of HIV infection.
- 17. Significant renal disease (primary or secondary) (for example severe renal impairment (CLCR < 30 mL/min).
- 18. Bodyweight < 50 kg.
- 19. Indication of liver disease, defined by serum levels of either ALT (SGPT), AST (SGOT), or alkaline phosphatase above 3x upper limit of normal (ULN) as determined during screening.
- 20. History of neurologic (e.g. stroke, seizure without a clear and resolved etiology, concussion accompanying loss of consciousness) or psychiatric condition that the investigator deems may interfere with interpretability of data.
- 21. History of malignancy within the last 5 years, except for basal cell carcinoma.
- 22. Planned elective surgery requiring general anaesthesia, or hospitalisation during the study period.
- 23. Significant history of drug dependence (with the exception of nicotine dependence) or abuse (including alcohol, as defined in DSM-V or in the opinion of the investigator) within the last two years prior to informed consent, or a positive urine drug screen for cocaine, opioid, phencyclidine (PCP), amphetamine or marijuana at screening.
- 24. Clinically significant uncompensated hearing loss in the judgment of the investigator. Use of hearing aids is not allowed.
- 25. Known hypersensitivity to drug product excipients (gelantin, povidone K25, lactose monohydrate, microcrystalline cellulose, pregelatinized starch, hydroxypropylcellulose, croscarmellose sodium, magnesium stearate, hypromellose, propylene glycol, titanium dioxide, talc and iron oxide yellow).
- 26. Participation in another trial with an investigational drug or procedure within 30 days prior to screening or previous participation in any BI 409306 study.
- 27. Any evidence of a clinically relevant concomitant disease, or clinical condition that in the opinion of the investigator would jeopardize patient's safety while participating in this trial.
- 28. Subjects not willing or able to comply with the protocol requirements or considered unreliable by the Investigator concerning the requirements for follow-up during the study and/or compliance with study drug administration.

Doc. No.: c02218444-07 Trial Protocol Revision 3 Page 32 of 101

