*D.C. + 11 1 1 C. +				1: 0			 			 	l	l					71

Treatment Day 1 and 14: Blood Sampling for Pharmacokinetic and Vital Signs

Planned Time (h:min)	-2:00	0:00	0:20	0:30	0:45	1:00	1:30	2:00	4:00	6:00
Clock Time (h:min)	Pre-dose	8:00 (dosing)	8:20	8:30	8:45	9:00	9:30	10:00	12:00	14:00
PK Sample	X		X	X	X	X	X	X	X	X
Vital Signs ¹³ (Day 1 only)	X ¹³		X ¹³	X ¹³	X ¹³		X ¹³			

Proprietary confidential information.

^{*} Refer to table below for timing of intensive PK sampling for Days 1 and 14.

**Home visits may be conducted for these visits in lieu of study center visits (cf. Section 6.1).

Page 6 of 101

Footnotes:

- 1. Screening to be performed within 3-28 days before drug administration, including body weight, height, smoking and alcohol history, and also an abbreviated visual exam per exclusion criteria (cf. Section 3.3.3).
- 2. In-patient stay is optional. If feasible for in-patient stay, the following procedures would apply: eligible study participants will be admitted to the study center in-patient facility for overnight stays. All CIAS subjects will remain in-patient for the duration of the treatment period, starting on Day -2 and will be allowed to leave after the last study procedure and after their fitness has been confirmed by the investigator on Day 14. AD subjects and healthy volunteers will check into clinic on Day -2 and remain in-patient till Day 1, return for daily visits till Day 12, and check into clinic again on Day 13 to Day 14. If there is a need that required AD subjects to remain in-patient, then the CIAS schedule plan may be utilized, per investigator discretion.
- 3. Vital signs will be collected via orthostatic measurements of systolic/diastolic blood pressure and pulse rate supine after 5 minutes rest, immediately after standing up and again after 3 minutes standing (cf. Section 5.2.6).
- 4. Vital signs and ECGs should be completed before dosing (pre-dose) and PK blood draws. Pre-dose is within 2 hours before the dose is given.
- 5. Serum pregnancy tests will be performed at specified study visits on female subjects of child-bearing potential except for CIAS subjects staying in-patient. In addition, urine (dipstick) pregnancy tests will be performed at Visit 2. Only those female subjects with a negative urine pregnancy test will receive study medication at Visit 3 (Day 1).

6.

7. Time of last meal before drug administration will be recorded on PK blood draw Days 1 and 14.

8.

9.

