No studies have been done with BI 409306 in pregnant women or women who are nursing their infants. It is unknown if BI 409306 is safe for pregnant women, unborn babies and infants who are nursing. It is unknown either if BI 409306 has an effect on sperm or eggs. Hence, female subjects who are nursing or pregnant are not allowed to join the study. Female subjects who are of child-bearing potential must accept to use a reliable form of birth control throughout the trial and follow-up period.

A potential effect of BI 409306, a centrally acting compound, on suicidality cannot be ruled out. Therefore, suicidality monitoring will be performed pre-dose and throughout the study to ensure that potential suicidality will be recognized in order to apply appropriate action.

This is an experimental drug at an early stage of testing and therefore an individual benefit cannot be guaranteed. The study procedures (e.g. ocular assessments, safety and suicidality

Boehringer Ingelheim 22 February 2017 BI Trial No.: 1289.27

Doc. No.: c02218444-07 Trial Protocol Revision 3 Page 24 of 101

monitoring, etc.) may in fact benefit the patients e.g. intensive medical care, a potentially better knowledge of the underlying disease which may lead to a better handling of AD and CIAS patients. Even if there is no direct benefit for the subjects during participation in this trial, it can be assumed that the trial results may contribute to better drug development in future.

This study will explore the ophthalmologic changes with respect to the visual acuity effects and other neurophysiological changes in order to further investigate the safety, tolerability and pharmacokinetics of the doses of BI 409306 (25 mg and 100 mg) that were already established to be within the safety margin of therapeutic dose.

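### Exclusion criterion 15 applies its nursing and contraception conditions only to women who menstruated within a year of consent, which is narrower than the rule in Section 2.3.

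*Protocol*

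**What the plan says.** Exclusion 15 in Protocol Section 3.3.3 opens its part for women with "Pre-menopausal women (last menstruation ≤1 year prior to informed consent) who". Two bullets hang from that clause. The first covers nursing or pregnancy. The second covers women of child-bearing potential without acceptable contraception, with a commitment lasting until 28 days after the last dose.

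Section 2.3 states the same safety rule without any reference to menstruation. On nursing and pregnancy: "Hence, female subjects who are nursing or pregnant are not allowed to join the study". On contraception: "Female subjects who are of child-bearing potential must accept to use a reliable form of birth control throughout the trial and follow-up period". Its reason is given just before: "It is unknown if BI 409306 is safe for pregnant women, unborn babies and infants who are nursing". Section 1.2.2 adds that female reproductive toxicity has not yet been assessed.

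Section 6.2.2 makes eligibility depend on meeting all inclusion criteria and no exclusion criterion. Section 8.3.1 asks for documented evidence against those criteria before a subject is allocated to treatment.

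**The concern.** The two sections cover different women. A woman whose last period was more than a year before consent falls outside both bullets of exclusion 15, even if she is nursing or still able to conceive. Section 2.3 covers her in either case. Because entry turns on the numbered criteria, a site could document her as eligible while the benefit-risk section bars her or requires contraception of her.

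At stake is exposure of a nursing infant, or of a pregnancy that contraception was meant to prevent, to a drug whose safety there is unknown. This is a matter of participant and infant safety, not of inference. It concerns only the opening condition of criterion 15, not how the contraception conditions inside the second bullet are joined.

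**Working it through.** No power, sample-size or error-rate figure is involved, so the check is a comparison of texts plus three small sums.

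**Who is covered**

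| Woman | Section 2.3 | Exclusion 15 as worded |
|---|---|---|
| Nursing, last period within 1 year of consent | Barred | Excluded |
| Nursing, last period over 1 year before consent | Barred | Not reached |
| Child-bearing potential, last period within 1 year | Must use birth control | Excluded if she does not |
| Child-bearing potential, last period over 1 year before | Must use birth control | Not reached |

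**Does another provision close the nursing gap?**

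- Exclusion 27 begins "Any evidence of a clinically relevant concomitant disease, or clinical condition that in the opinion of the investigator would jeopardize" and goes on to the safety of the patient, not of her infant.
- Exclusion 28 begins "Subjects not willing or able to comply with the protocol requirements" and concerns compliance and reliability. A nursing woman may be willing and able to attend visits and take the drug.
- The scheduled tests detect pregnancy, not nursing.
- The withdrawal rules in Section 3.3.4.1 name pregnancy, not nursing.

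**Does another provision close the contraception gap?** Only indirectly. A woman who refuses birth control fails a protocol requirement and so meets exclusion 28, but the list does not tell the site to ask her.

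**Is pregnancy at entry covered?** Largely. Flow Chart footnote 5 says "Serum pregnancy tests will be performed at specified study visits on female subjects of child-bearing potential", with an exception for CIAS in-patients. It also allows the first dose only after a negative urine test. Neither depends on the date of the last period. Section 3.3.4.1 withdraws a woman who becomes pregnant.

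**When the nursing gap opens.** Assume delivery 37 to 42 weeks after the last period (the documents give no figure) and no return of periods. Then 52 weeks since the last period is reached at:

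- 52 − 42 = 10 weeks post-partum
- 52 − 40 = 12 weeks post-partum
- 52 − 37 = 15 weeks post-partum

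This shows when such a woman leaves the scope of exclusion 15, not how often it happens.

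**Where affected women would mainly be found.** Schizophrenia patients plus their age-comparable volunteers: 20 + 10 = 30 of 60 planned subjects, in the 18 to 55 age range. The sex split is not given, and those affected would be a small part of the women among the 30.

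**Length of the commitment.** Day 14 + 28 days = Day 42. The End of Trial visit falls 7 to 14 days after the last dose, that is Day 21 to Day 28. On duration, then, exclusion 15 is not the weaker text. It is narrower only in which women it reaches.

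**The case against.** The strongest reply is that Section 2.3 is itself mandatory, and Section 8 requires the trial to follow the whole protocol. Exclusion 15 does not permit a nursing woman to enter; it is silent about a rare subgroup that another section bars. The governing word is pre-menopausal, and a woman without periods because she is nursing is pre-menopausal in the ordinary sense. On that view the parenthesis is a drafting slip meant to separate out post-menopausal women. If exclusion 28 reaches Section 2.3 for contraception, it arguably does so for nursing as well. The consent form, site file and eCRF eligibility pages are not available here and may carry the instruction.

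Much of this stands as a limit on the consequence. An investigator who applies Section 2.3 would exclude the nursing woman. A woman who refuses contraception meets exclusion 28. A woman without periods because of an accepted hormonal method already complies. What sites do in practice cannot be judged from these documents.

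It does not remove the mismatch. The parenthesis attaches a calendar cut-off to the ordinary word, and the available text defines neither menopause nor child-bearing potential elsewhere. The wider rule in Section 2.3 confirms that the two sections disagree. Reading exclusion 28 to catch nursing works only if the site has already gone to Section 2.3 for the bar, which is what the eligibility list should make unnecessary.

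**Conclusion.** The concern holds: as worded, exclusion 15 covers fewer women than the safety rule it is meant to implement. The nursing gap is the clearer of the two, since no other criterion, test or withdrawal rule addresses nursing. The contraception gap is one of wording in the list, partly backed by exclusion 28. Pregnancy at entry is not part of the finding.

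The size is small. No count can be derived, and the number is probably very few. The conclusion rests on reading the parenthesis literally and on the listed criteria deciding entry, as Sections 6.2.2 and 8.3.1 say. Only the 10 to 15 week illustration depends on an assumed length of pregnancy. Endpoints, analysis sets and summaries do not change. It should be corrected, although its rarity lowers the urgency.

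**What to change.** Reword the part of exclusion 15 that concerns women in two steps. First, exclude any female subject who is nursing or pregnant, whatever the date of her last period. Second, apply the contraception condition to all women of child-bearing potential, in line with Section 2.3. State that absence of periods for a reason other than menopause does not count as post-menopausal. How menopause is established is for the sponsor's clinical team.

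The cost is one sentence in the next amendment, with the ethics and authority approval that Section 8.1 requires of any amendment, and a contraception statement from at most a few more women. The rewording needs no new procedure. If the sponsor chose to confirm menopause by a laboratory test, that would be an addition, because Table 5.2.3: 1 lists none.

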- c. Male or female patients age 55 to 85 years, who have not been taking acetyl cholinesterase inhibitors (donepezil, galantamine, rivastigmine) and/or memantine for at least 3 months or on stable dose of acetyl cholinesterase inhibitors (donepezil, galantamine, rivastigmine) and/or memantine at least 3 months before randomization. Patients older than 85 years may be included based on an acceptable general health status, (e.g. concomitant diseases, physical capability to follow the required study procedures [visits etc.]) per investigators judgement.
- d. Availability of a pre-existing cranial computer tomography (CCT) or magnetic resonance imaging (MRI) scan of the brain (initiation of radiological imaging is not required) not older than one year prior to screening; if not available, a CCT must be performed at screening. Results of radiological brain imaging must be compatible with Diagnosis of Alzheimer Disease and exclusion of relevant signs indicative of potential vascular dementia (see also exclusion criteria).
- e. If needed, a caregiver may be present during site activities.

OR

Age-comparable male or female healthy volunteers age 18 to 85 years. Healthy volunteers older than 85 years may be included based on an acceptable general health status, (e.g. concomitant diseases, physical capability to follow the required study procedures [visits etc.]) per investigators judgement:

- a. After 10 patients with schizophrenia (as described above) are entered into the study, the median age of the group will be computed. Five healthy volunteers at or below the median age but greater than 18 years old (low age group) and five healthy volunteers above the median but less than 55 (high age group) will be entered into the study.
- b. Similarly, after 10 patients with AD are entered, the median age will be computed. Five healthy volunteers at or below the median age but greater than 55 years old (low

Proprietary confidential information.

age group) and five healthy volunteers above the median (high age group) will be entered into the study.

- 2. Subjects must exhibit reliability and physiologic capability, per investigator judgment, to comply with all protocol procedures.
- 3. Signed and dated written informed consent by date of Visit 1 in accordance with GCP and the local legislation. If the patient needs a legal representative, then this legal representative must give written informed consent as well.

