6.2.2 Treatment periods

If the patient/healthy volunteer has completed screening and has been determined potentially eligible by the investigator, the following baseline investigations will be performed on Day - 2 and/or -1:

- Physical examination including vital signs
- •
- Review Adverse Events (AEs) and Concomitant Therapies (CTs)
- Clinical laboratory/urinalysis
- Review Inclusion/Exclusion criteria

•

Subjects, who meet all the inclusion criteria, and none of the exclusion criteria, will be eligible for the study. Eligible subjects will be randomized (cf. Section 4.1.2).

Each randomized participant will receive study medication daily from Day 1 through 14 according to the Flow Chart. Study drug will be taken orally in the morning of each treatment day under direct supervision of the investigator or designee.

Boehringer Ingelheim BI Trial No.: 1289.27 Doc. No.: c02218444-07 22 February 2017

Page 59 of 101

The measurements performed during the treatment period are specified under Section 5.2 of this protocol and Flow Chart.

Trial Protocol Revision 3

For details on time points for collection of plasma samples for PK analysis, cf. Flow Chart and Sections 5.5.1 and 5.5.2.

In general, if several measurements including venipuncture are scheduled for the same point of time, venipuncture should be the last of the measurements due to its inconvenience to the patient and possible influence on physiologic parameters.

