6.2.3 End of trial and follow-up period

The End of Trial visit will be performed 7 to 14 days after last drug administration. EOT evaluation will include a physical exam, vital signs, 12-lead ECG, standard laboratory tests, and review of AEs and CTs.

All clinically significant abnormal values (including laboratory parameters) will be followed up using the appropriate tests until a return to a medically acceptable level is achieved.

All (S)AEs, including those persisting after trial completion must be followed up until they have resolved, have been sufficiently characterized, or no further information can be obtained.

In case of premature discontinuation from the 14 day treatment, (e.g. removal of patient from treatment due to AE or abnormal laboratory test result), the EOT visit should be performed within 7 days of last intake of study drug.

BI Trial No.: 1289.27

Doc. No.: c02218444-07 Trial Protocol Revision 3 Page 60 of 101

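### Exclusion 15 joins refusal of pregnancy testing to the contraception conditions with *and*, so read literally it admits a woman who plans to stop contraception during the trial but accepts testing

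*Protocol*

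**What the plan says.** Protocol Section 3.3.3, Exclusion 15, covers pre-menopausal women. After nursing and pregnant women, it turns to women of child-bearing potential and gives three conditions in one sentence:

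- they are not using an acceptable contraceptive method;
- they do not intend to keep using it up to 28 days after the last dose;
- "and do not agree to submit to periodic pregnancy testing during participation in the trial".

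The first two are joined by *or*, the third by *and*.

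The limb for men reads: "Men who are able to father a child, unwilling to be abstinent or use adequate contraception for the duration of study participation", and runs to at least 28 days after treatment. It carries no second condition.

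The benefit-risk assessment (Section 2.3) states the requirement for women without qualification: "Female subjects who are of child-bearing potential must accept to use a reliable form of birth control throughout the trial and follow-up period".

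Section 6.2.2 makes the listed criteria decisive: "Subjects, who meet all the inclusion criteria, and none of the exclusion criteria, will be eligible for the study".

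**The concern.** Section 2.3 makes contraception compulsory and does not offer testing as an alternative. As printed, Exclusion 15 can let agreement to testing stand in for contraception.

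Testing is a poor substitute. The Flow Chart marks pregnancy tests at screening, baseline, Day 7 and Day 14, and none at the End of Trial visit. Its footnote 5 waives the serum tests for schizophrenia (CIAS) subjects who stay in-patient. A test detects a pregnancy; it does not prevent exposure. Section 1.2.2 records that female reproductive toxicity has not yet been assessed.

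What is at stake is participant safety and consistent screening across sites in a multi-centre trial. No estimate or analysis depends on it.

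**Working it through.** No figure in the plan is involved, so the check is a truth table on the wording.

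**Conditions** (Exclusion 15)

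- P: of child-bearing potential
- N: not using an acceptable method
- S: does not plan to continue to 28 days after the last dose
- R: refuses periodic pregnancy testing

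The printed order is P *and* N *or* S *and* R. It can be grouped in four ways. The second follows the commas.

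**Women tested** (P true for all)

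- Case 1: uses contraception now, will stop before End of Trial, accepts testing (N false, S true, R false)
- Case 2: uses none and will not start, accepts testing (N true, S true, R false)
- Case 3: uses and will continue, refuses testing (N false, S false, R true)

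| Grouping | Case 1 | Case 2 | Case 3 |
|---|---|---|---|
| (P and N) or (S and R) | not excluded | excluded | not excluded |
| P and (N or S) and R | not excluded | not excluded | not excluded |
| P and (N or (S and R)) | not excluded | excluded | not excluded |
| ((P and N) or S) and R | not excluded | not excluded | not excluded |
| With *or*: P and (N or S or R) | excluded | excluded | excluded |

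Case 1 is missed under all four groupings, so the finding does not depend on choosing one. Case 2 is missed under two of the four. Case 3 is missed by this criterion under all four. The fully compliant woman (N, S and R all false) stays eligible under every row, including the corrected one.

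**When Case 1 conflicts with Section 2.3.** The last dose is on Day 14. By Section 6.2.3, "The End of Trial visit will be performed 7 to 14 days after last drug administration", that is Day 14 + 7 = Day 21 to Day 14 + 14 = Day 28. The limit in Exclusion 15 is Day 14 + 28 = Day 42. A woman who plans to stop before End of Trial conflicts with Section 2.3. One who plans to stop only between End of Trial and Day 42, an interval of 28 − 14 = 14 to 28 − 7 = 21 days, is within the trial and follow-up requirement and is not counted here. Nor is a woman using nothing now who is willing to start.

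**Who could be concerned.** The groups aged up to about 55 are 20 CIAS patients and 10 healthy volunteers chosen to be comparable with them: 20 + 10 = 30 of 60 subjects, men and women together. This assumes few women aged 55 or older meet the pre-menopausal definition. The number of women of child-bearing potential is not stated.

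**The case against.** The strongest reply is that eligibility does not rest on Exclusion 15 alone. Exclusion 28 removes "Subjects not willing or able to comply with the protocol requirements". If the *must* in Section 2.3 is a protocol requirement, a woman who intends to stop contraception is unwilling to comply and is ineligible at entry. Inclusion 2 points the same way: "Subjects must exhibit reliability and physiologic capability, per investigator judgment, to comply with all protocol procedures". A woman who refuses testing also fails in practice, because footnote 5 requires a negative urine test before Day 1 dosing, and Section 3.3.4.1 withdraws anyone who becomes pregnant.

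A second reply is that *and* may be additive, introducing one more kind of woman to be excluded. Under the comma grouping, any woman who accepts testing passes whatever her contraception. That would make the 28-day limit and the list of acceptable methods nearly pointless, so the sponsor can hardly have meant it.

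Much of this stands. The intent is clear, the additive reading would close the gap, and Exclusion 28 can act before randomisation. The contrast with the male limb is only supporting evidence, since a testing condition could not apply to men.

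It does not remove the fault. The sentence uses *or* for alternatives and then changes to *and*, with nothing to signal an additive sense. Exclusion 28 reaches Case 1 only if the site lets a sentence in the benefit-risk narrative override the narrower criterion written for exactly this question. Section 8.3.1 requires documented evidence that no exclusion criterion is met, so sites will check the printed words.

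**Conclusion.** The concern holds as a drafting fault in an operative safety criterion. On any literal grouping, Exclusion 15 fails to exclude a woman who uses contraception now, will stop before End of Trial and accepts testing, contrary to Section 2.3. Whether it also passes a woman using no contraception depends on the grouping.

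The size is small: an unstated number of women, drawn from about 30 of 60 subjects under the age assumption above, with general safeguards that should catch most of them. The conclusion rests on reading the connectives as printed; it does not claim that the sponsor intended the gap. No endpoint, sample size or analysis is affected. The wording should still be corrected, because the drug has no female reproductive toxicity assessment and the remedy is trivial.

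**What to change.** In Exclusion 15, change the *and* before the pregnancy-testing condition to *or*. Better, under the heading of child-bearing potential, list three separate alternatives, any one of which excludes:

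- no acceptable contraceptive method in use;
- no plan to continue it until 28 days after the last dose;
- no agreement to periodic pregnancy testing.

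Either version excludes all three cases in the table and keeps the compliant woman eligible. The cost is one word, or three bullets, in a protocol amendment. The SAP's analyses need no change.
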